### **5.3.3. Other Safety Analyses**

ECG measurements will include heart rate, QT interval, Fredericia-corrected QT interval (QTcF), PR interval, and QRS interval. Change from baseline will be summarized descriptively by treatment group at each scheduled evaluation and all ECG data will be listed. Proportion of subjects with abnormal ECG interpretations will be summarized at each study visit and by treatment group. Proportion of subjects who meet each of the following criteria from International Conference on Harmonization Guideline E14 “Clinical Evaluation of QT/QTc Interval Prolongation and Proarrhythmic Potential for Non-Antiarrhythmic Drugs” (October 2005) for QT and corrected QT intervals will be summarized across treatment groups:

- QT or QTcF >450 msec
- QT or QTcF >480 msec
- QT or QTcF >500 msec
- QT or QTcF increases from baseline by  $\geq 30$  msec
- QT or QTcF increases from baseline by  $\geq 60$  msec

### **5.3.4. Open-Label Extension Safety Analyses**

Adverse events, laboratory values, and vital signs will be used in the OLE period to assess safety. Results occurring in just the OLE period will be reported based on the same treatment groups used for reporting during the DB portion of the study. The same analyses planned for the DB period will be generated for the OLE. Additionally, pooled AE displays will be developed. For the pooled analysis, only AEs in the OLE would apply to the patients randomized to vehicle during the DB

portion of the study. For patients randomized to ATI-502 during the DB portion, their complete AE profile for the entire study should be summarized in the pooled analysis.

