#### **Double-blind (DB) Period:**

A total of 120 subjects will be randomized in a 1:1:1 ratio:

- Vehicle Topical Solution BID for 24 weeks (6 months)
- ATI-50002 Topical Solution, 0.12%, BID for 24 weeks (6 months)
- ATI-50002 Topical Solution, 0.46%, BID for 24 weeks (6 months)

During the screening period, subjects will be assessed for eligibility into the study. Subjects will apply up to 4 mL of study medication to the entire scalp or patchy areas with a ½” margin twice a day for 24 weeks. Assessment of response to treatment will be performed at Week 4 (Visit 5), Week 8 (Visit 6), Week 12 (Visit 7), Week 16 (Visit 8), Week 20 (Visit 9), Week 24 (Visit 10), and post-treatment Week 28 (Visit 11). Safety and tolerability will be evaluated at each study visit by assessment of adverse events and vital signs, and at select visits, ECGs and clinical laboratory tests will be completed. The primary analysis will be conducted after all subjects complete Visit 10 or Visit 11 of the double-blind period.

Subjects who complete Visit 10 or Visit 11 (Week 24 or 28) will be eligible to enter a 28 week OLE. Subjects who decline or are not eligible for the OLE should be seen for the Visit 11 (Post-treatment) assessments.

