#### **Open-Label Extension (OLE):**

In the OLE, safety, tolerability and efficacy will be assessed. All subjects enrolled in the OLE will apply ATI-50002 Topical Solution, 0.46% to the entire scalp or patchy areas with a ½” margin, twice daily for 24 weeks (6 months). In addition, subjects with eyebrow loss may apply study

medication to the entire eyebrow(s) twice daily for 24 weeks. Subjects will be followed for safety, tolerability and efficacy as detailed in Section 1.2 Schedule of Assessments. Subjects who entered the OLE and for administrative reasons had a gap of > 30 days between completion of Visit 10 or Visit 11 and entry into the open-label should return for the OLE Visit 1 and have the procedures detailed in the Schedule of Assessments.

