## **5. STATISTICAL METHODS**

Descriptive statistical methods will also be used to summarize the data from this study, with hypothesis testing performed for the primary and key secondary efficacy endpoints. Unless stated otherwise, the term “descriptive statistics” refers to number of subjects, mean, median, standard deviation, minimum, and maximum for continuous data, and frequencies and percentages for categorical data. For categorical variables, the denominator of percentages will be the number of subjects in the treatment group, except for those collected by study visit and/or scheduled time point, in which case the denominator of percentages will be the number of subjects with a non-missing value at the visit and/or the scheduled time point. If a different denominator is used, this will be identified in the summary table.

All data collected during the study will be included in data listings. Unless otherwise noted, the data will be sorted first by treatment group, subject number, and then by date within each subject number. Assessments indicated as ‘Not Done’ will not be included in the listings.

The term ‘treatment group’ refers to ATI-50002 active groups and matching Vehicle group.

All statistical testing will be two-sided and will be performed using a significance (alpha) level of 0.05 unless otherwise stated. P-values will be presented to three decimal places. For the efficacy endpoints, the ATI-50002 treatment groups will be tested versus vehicle via statistical inference.

The statistical analyses will be conducted with the SAS® software package version 9.4 or higher. All analyses will be subject to formal verification procedures. Specifically, results will be independently verified by a second programmer/statistician or independently hand-checked prior to issuance of the draft statistical report. All documents will be reviewed by the lead statistician to ensure accuracy and consistency.

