#### **5.3.1. Adverse Events**

Adverse events will be mapped to a preferred term and system organ classification by Medical Dictionary for Regulatory Activities (MedDRA) version 22.0.

An overall summary will be presented which includes the number of TEAEs and the number and percentage of subjects who experienced at least one TEAE. This summary will also include:

- Any TEAE
- Any Serious TEAE
- Any Mild TEAEs
- Any Moderate TEAEs
- Any Severe TEAEs
- Any Related TEAEs
- Any TEAEs leading to discontinuation
- Any Related TEAEs leading to discontinuation

Additional summaries of TEAEs will be provided showing the number and percentage of subjects who experienced at least one TEAE. These summaries will be presented by system organ class (SOC), preferred term (PT) and maximum severity. If a participant reports the same PT multiple times within the same SOC, that PT will only be counted once within that SOC for that participant. As with the PT, if a participant reports multiple conditions within the same SOC, that SOC will only be counted once for that participant. In the summary, SOC will be listed in ascending alphabetical order; PTs will be listed in order of descending frequency for all participants within each SOC.

The occurrence of TEAEs related to study medication (possibly/probably) will be tabulated by SOC, PT and maximum severity. Serious adverse events (SAE) will be presented by system organ class (SOC), preferred term (PT) and maximum severity. SAE related to study medication will also be presented by SOC and PT.

All AEs reported will be listed by individual subject, showing both verbatim and preferred terms. All AEs reported with a start date prior to the initiation of study medication will be excluded from the TEAE tables but will be included in the listings.

Missing onset dates will be imputed as previously outlined in Section 3.3.5 as required to determine TEAEs.

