### Section 14.3 Safety

17. Overall Summary of Adverse Events, Safety Population
18. Treatment-Emergent Adverse Events by System Organ Classification, Preferred Term, and Greatest Severity, Safety Population
19. Treatment-Emergent Adverse Events by System Organ Classification and Preferred Term, Safety Population
20. Treatment-Emergent Serious Adverse Events by System Organ Classification and Preferred Term, Safety Population
21. Treatment-Emergent Adverse Events Related to Study Medication by System Organ Classification and Preferred Term, Safety Population
22. Treatment-Emergent Adverse Events Leading to Discontinuation of Study Medication by System Organ Classification and Preferred Term, Safety Population

23. Overall Summary of Adverse Events, Safety Population (Pooled DB and OLE)
24. Treatment-Emergent Adverse Events by System Organ Classification, Preferred Term, and Greatest Severity, Safety Population (Pooled DB and OLE)
25. Treatment-Emergent Adverse Events by System Organ Classification and Preferred Term, Safety Population Safety Population (Pooled DB and OLE)
26. Treatment-Emergent Serious Adverse Events by System Organ Classification and Preferred Term, Safety Population (Pooled DB and OLE)
27. Treatment-Emergent Adverse Events Related to Study Medication by System Organ Classification and Preferred Term, Safety Population (Pooled DB and OLE)
28. Treatment-Emergent Adverse Events Leading to Discontinuation of Study Medication by System Organ Classification and Preferred Term, Safety Population (Pooled DB and OLE)
29. Summary of Hematology Results and Change from Baseline by Visit, Safety Population
30. Summary of Treatment-Emergent Abnormal Hematology by Visit, Safety Population
31. Summary of Serum Chemistry Results and Change from Baseline by Visit, Safety Population
32. Summary of Treatment-Emergent Abnormal Serum Chemistry by Visit, Safety Population
33. Summary of Urinalysis by Visit, Safety Population
34. Summary of Treatment-Emergent Abnormal Urinalysis by Visit, Safety Population
35. Summary of Vital Signs and Change from Baseline, Safety Population

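### The pooled double-blind plus open-label AE tables mix about 24 weeks of observation on drug with up to about 48 weeks, and report crude percentages with no time base

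*SAP*

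**What the plan says.** SAP 1.1 plans 24 weeks of double-blind treatment, then an optional OLE in which all participants apply the 0.46% solution for 24 weeks.

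SAP 5.3.4 plans OLE-only safety results by double-blind treatment group and, in addition, pooled AE displays. In the pooled displays "only AEs in the OLE would apply to the patients randomized to vehicle during the DB" portion of the study. For subjects randomized to active drug, "their complete AE profile for the entire study should be summarized in the pooled analysis".

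SAP 5.3.1 sets the summary statistics. The overall table gives the number of TEAEs and the number and percentage of subjects with any. Beyond that: "Additional summaries of TEAEs will be provided showing the number and percentage of subjects who experienced at least one TEAE". Under SAP 5, for data not collected by visit, "the denominator of percentages will be the number of subjects in the treatment group".

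SAP 8.2 lists the pooled tables as items 23-28, all on the Safety Population, which SAP 4.2 defines as randomized subjects with at least one application. Exposure appears only as a separate table (item 7). The columns of the pooled tables are not specified. The nearest rule is SAP 3.3.7, under which safety results are summarized by treatment group.

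**The concern.** A crude percentage of subjects with at least one event rises with the length of observation. The pooling rule gives the randomized groups different lengths by design, and no planned statistic corrects for it. A reader of items 23-28 could not separate a higher event rate from a longer period of looking.

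This matters because long-term safety and tolerability of the 0.46% solution is a stated objective (Protocol 4.4, SAP 2), and items 23-28 are the only planned AE tables that span both periods. What is at stake is the reading of a descriptive safety table. No efficacy result or hypothesis test is involved.

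**Working it through.** Neither document gives an AE incidence or an OLE uptake, so there is no figure of the plan's own to reproduce. Both are assumed below and varied.

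**Inputs from the documents.** Double-blind treatment is 24 weeks (168 days) and OLE treatment is 24 weeks (SAP 1.1). The TEAE window runs to 31 days after last dose (SAP 3.3.6). About 40 subjects are planned per group (SAP 3.1).

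**Assumptions.** The hazard *h* is constant and the same in every group; *p* is the 24-week incidence; *f* is the fraction entering and completing the OLE, equal across groups.

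**1. Planned time on active drug.** Former vehicle: 24 weeks. Former active: 24 + 24 = 48 weeks if they enter the OLE, otherwise 24, so the group mean is 24(1 + *f*); at *f* = 0.5 this is 36 weeks.

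**2. Columns by randomized group, full uptake.** The 48-week incidence is 1 − (1 − *p*)².

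| Assumed 24-week incidence | Over 48 weeks |
|---|---|
| 5% | 9.8% |
| 10% | 19% |
| 20% | 36% |
| 30% | 51% |
| 50% | 75% |

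**3. With the 31-day tail and no gap.** Observation is 168 + 31 = 199 days against 336 + 31 = 367 days, a ratio of 1.84. If 20% is the incidence over 199 days, the longer window gives 1 − 0.8^1.84 = 33.7%.

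**4. Partial uptake, *p* = 20%.** Former active = *f* × 36% + (1 − *f*) × 20%. Former vehicle is 20% if only OLE entrants are counted. It is *f* × 20% if the whole Safety Population stays in the denominator, as the table titles literally read.

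| *f* | Former active | Former vehicle, OLE entrants | Former vehicle, whole Safety Population |
|---|---|---|---|
| 0.5 | 28.0% | 20% | 10% |
| 0.7 | 31.2% | 20% | 14% |
| 0.9 | 34.4% | 20% | 18% |
| 1.0 | 36.0% | 20% | 20% |

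**5. One combined active-drug column instead.** There is no contrast between groups, but the percentage has no fixed time base. At *f* = 1: (80 × 36% + 40 × 20%)/120 = 30.7%, over a mean of (80 × 48 + 40 × 24)/120 = 40 weeks. At *f* = 0.5, with 80 former active and 20 former vehicle subjects: (80 × 28% + 20 × 20%)/100 = 26.4%, over a mean of (40 × 48 + 60 × 24)/100 = 33.6 weeks. The hazard is the same; the percentage moves with uptake.

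**6. Exposure-adjusted rate, *p* = 20%.** *h* = −ln(0.8)/24 = 0.0093 per week. Mean time at risk to first event or end of observation is 0.20/*h* = 21.5 weeks over 24 weeks and 0.36/*h* = 38.7 weeks over 48. The rates are 0.20/21.5 and 0.36/38.7, both 0.93 per 100 subject-weeks. The artificial gap disappears.

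**7. Departure from constant hazard.** If all events fell in the first 24 weeks on drug, both groups would show 20% and the gap would be zero. Early-onset events such as application-site reactions lie between that and step 2.

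**The case against.** The strongest reply is that the side-by-side contrast is inferred. SAP 5.3.4 specifies no columns for the pooled displays. Counting vehicle subjects only from their first active drug suits a single column for any ATI-50002 exposure at least as well, and SAP 3.3.7 is only a general rule. This stands as far as it goes: the group gaps in steps 2 to 4 are conditional on columns by group. The missing time base remains under either layout (step 5).

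Four stronger readings are tempting, and the documents do not support them.

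- *Former active subjects will show 9 to 21 points more events.* Those are the gaps for 10% to 30% incidence in step 2. They need a constant hazard and every active subject entering and completing an optional OLE with entry criteria. At 20% incidence and 50% uptake the gap is 8 points, counting only OLE entrants among former vehicle subjects.
- *Subject percentages are the only AE summary.* The overall table also counts TEAEs, although that count has no time base either.
- *The plan offers no fair comparison.* The double-blind tables (SAP 8.1, items 78-84) and the OLE-only tables (SAP 8.2, items 17-22) each cover a matched planned 24 weeks.
- *Long drug-free gaps inflate the former-active count.* Items 24-28 are TEAE tables, and item 23 follows a TEAE-based summary. The 31-day windows exclude later gap events until OLE dosing starts. What remains is an ambiguity: no TEAE window is stated for the pooled set, and SAP 5.3.4 asks for the complete profile.

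It is also fair that starting vehicle subjects' count at first active drug is sensible in itself. What is missing is a denominator to match.

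**Conclusion.** The point holds as a low-cost improvement to a descriptive display. By design, the pooled tables combine about 24 weeks on drug for former vehicle subjects with 24 to about 48 weeks for former active subjects, and give percentages and counts without person-time.

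If columns are by randomized group, an equal constant hazard and an assumed 24-week incidence of 20% give former-active figures of 28% to 36% against 20%, for uptake of 50% to 100%. Under the constant-hazard assumption the direction is the same for any uptake above zero. The size depends on incidence, uptake and event timing, none of which the documents give. If vehicle subjects who never enter the OLE stay in the denominator, the gap widens.

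A reader might infer that the trial's safety conclusions are biased. The documents do not support that: safety is descriptive, and the period-specific AE tables are unaffected.

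**What to change.** In SAP 5.3.4 and items 23-28 of SAP 8.2:

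- Keep the crude percentages and event counts, and state the table columns.
- Add exposure-adjusted incidence rates with 95% CI: subjects with a first TEAE divided by subject-years at risk, from first active dose to first event or the end of the TEAE window. Exclude drug-free gap time outside the SAP 3.3.6 windows. The denominator should be this time at risk, not time on drug, because the TEAE numerator includes the 31-day off-drug tail.
- State which TEAE window applies to the pooled set.
- Show total exposure in the column headers.
- Restrict the former-vehicle denominator to subjects with at least one OLE dose.

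The cost is some extra derivation. SAP 3.3.6 defines exposure days only for the double-blind period and sets OLE Day 1 at the Visit 10 date, whereas Protocol 5.5 dates the start of OLE treatment from OLE Visit 1. OLE person-time should therefore come from actual OLE dosing dates. The rates also assume a roughly constant hazard and can make longer-exposed groups look safer for early-onset events, which is one reason to keep the crude percentages beside them.

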**6. CHANGES IN THE PROTOCOL-SPECIFIED ANALYSES**

All analyses specified in the SAP are consistent with those specified in the protocol. Should any deviations from the analyses specified in the authorized statistical analysis plan arise, such deviations will be documented in the final clinical study report.

## 7. PROGRAMMING CONVENTIONS

- Page orientation, margins, and fonts: Summary tables, listings, and figures will appear in landscape orientation. There should be a minimum of a 1” boundary on the upper (bound) edge, and a minimum of a 1.0” boundary on the remaining three edges. Output should be printed in Courier New with a point size of 8. Titles may be printed using a larger font (e.g., Arial point size 10).
  - Identification of analysis population: Every summary table and figure should clearly specify the analysis population being summarized. Listings will be prepared for all subjects.
  - Group headers: In the summary tables, the group headers will identify the summary group and the sample size for the indicated analysis population. Of note, the header’s sample size does not necessarily equal the number of subjects summarized within any given summary module; some subjects in the analysis population may have missing values and thus may not be summarized.
  - Suppression of percentages corresponding to null categories: When count data are presented as category frequencies and corresponding percentages, the percent should be suppressed when the count is zero in order to draw attention to the non-zero counts.
  - Presentation of sample sizes: Summary modules should indicate, in one way or another, the number of subjects contributing to the summary statistics presented in any given summary module. As mentioned above, this may be less than the number of subjects in the analysis population due to missing data.
    - In the quantitative modules describing continuous variables (and thus presenting sample size, means, and standard deviations), the sample size should be the number of non-missing observations.
    - For categorical variables that are presented in frequency tables, the module should present the total count in addition to the count in each category. Percentages should be calculated using this total as the denominator, and the percentage corresponding to the sum itself (that is, 100%) should be presented to indicate clearly to a reviewer the method of calculation.
  - Sorting: Listings will be sorted by treatment group, subject number and date, if applicable.
  - General formatting rules: Rounding for all variables will occur only as the last step, immediately prior to presentation in listings, tables, and figures. No intermediate rounding will be performed on derived variables. The standard rounding practice of rounding numbers ending in 0-4 down and numbers ending in 5-9 up will be employed.
  - Numerical Values: The presentation of numerical values will adhere to the following guidelines:
    - Raw measurements will be reported to the number of significant digits as captured electronically or on the CRFs.
    - Standard deviations will be reported to two decimal places beyond the number of decimal places the original parameter is presented.
-

- Means will be reported to one decimal place beyond the number of significant digits as the parameter.
- Calculated percentages will be reported to one decimal place.
- Dates will be formatted as DDMMYY. Partial dates will be presented on data listings as recorded on CRFs.
- Time will be presented according to the 24-hour clock (HH:MM).

**8. PROPOSED TABLES, LISTINGS, AND FIGURES**  
**8.1. END OF DOUBLE-BLIND TREATMENT PERIOD ANALYSIS**

Section 14.1 Accountability and Baseline Characteristics

1. Table 14.1.1 Subject Disposition and Reasons for Early Termination, ITT Population
2. Table 14.1.2 Primary Protocol Violations, ITT Population
3. Table 14.1.3 Analysis Populations, ITT Population
4. Table 14.1.3.1 Reasons for Exclusion from Per Protocol Population, ITT Population
5. Table 14.1.4 Demographics, ITT Population
6. Table 14.1.5 Baseline Characteristics, ITT Population
7. Table 14.1.6 Previous Therapies for Patchy Alopecia, ITT Population
8. Table 14.1.6 Medical History, ITT Population
9. Table 14.1.7 Physical Examination at Screening, ITT Population
10. Table 14.1.8.1 Prior Medications, Safety Population
11. Table 14.1.8.2 Concomitant Medications, Safety Population
12. Table 14.1.9 Study Medication Exposure and Compliance, Safety Population

Section 14.2 Efficacy

SALT

13. Table 14.2.1.1 Summary of SALT Score, Change from Baseline, and Percent Change from Baseline by Visit (LOCF), ITT Population
14. Table 14.2.1.1a Summary of SALT Score, Change from Baseline, and Percent Change from Baseline by Visit (Observed), ITT Population
15. Table 14.2.1.2 Analysis of Percent Change from Baseline in SALT Score (LOCF), ITT Population
16. Table 14.2.1.3 Analysis of Percent Change from Baseline in SALT Score (LOCF), PP Population
17. Table 14.2.1.4 Analysis of Percent Change from Baseline in SALT Score (Observed), ITT Population
18. Table 14.2.1.5 Analysis of Percent Change from Baseline in SALT Score (Observed), PP Population
19. Table 14.2.1.6 Analysis of Percent Change from Baseline in SALT Score (LOCF), Exploratory MMRM, ITT Population
20. Table 14.2.1.7 Analysis of Percent Change from Baseline in SALT Score (LOCF), Exploratory MMRM, PP Population
21. Table 14.2.1.8 Analysis of Change from Baseline in SALT Score (LOCF), ITT Population

ALODEX

22. Table 14.2.2.1 Summary of ALODEX Score, Change from Baseline, and Percent Change from Baseline by Visit, ITT Population

- 23. Table 14.2.2.2 Analysis of Percent Change from Baseline in ALODEX (LOCF), ITT Population
- 24. Table 14.2.2.3 Analysis of Change from Baseline in ALODEX Score (LOCF), ITT Population

